5.1.2 Hypotheses and Statistical Methods for Secondary Objectives

5.1.2.1 Hypotheses

No hypotheses will be tested. Descriptive statistics will be presented.

5.1.2.2 Statistical Methods

5.1.2.2.1 For Secondary Objective 1

Thirty days^a after the administration of MenACYW conjugate vaccine or MENVEO[®], the hSBA geometric mean titer ratio (GMTR) between Group 1 and Group 2 will be calculated and 95% CI will be provided as follows.

Logarithm transformation of the individual titers will be calculated. Assuming that individual $\log_{10}(\text{titer})$ is normally distributed, the 95% CI for the difference in $\log_{10}(\text{GMT})$ between Group 1 and Group 2 will be in the form:

$$\bar{X}_1 - \bar{X}_2 \pm t(1 - \alpha/2, n_1 + n_2 - 2) \cdot S \sqrt{1/n_1 + 1/n_2}$$

where $\bar{X}_i = \log_{10}(\text{GMT})$ is the mean of $\log_{10}(\text{titer})$ of Group i ,

$S^2 = [(n_1 - 1) S_1^2 + (n_2 - 1) S_2^2] / (n_1 + n_2 - 2)$ is the pooled sample variance,

n_i and S_i^2 are the sample size and sample variance of Group i ,

$t(1 - \alpha/2, n_1 + n_2 - 2)$ is the 100(1- $\alpha/2$) percentile of the t -distribution with degrees of freedom $df = n_1 + n_2 - 2$.

The 95% CI for the hSBA GMTR between Group 1 and Group 2 will be formed by taking the antilogarithms of the lower and upper limits of the 95% CI for the difference in $\log(\text{GMT})$ between both vaccine groups.

5.1.2.2.2 For Secondary Objective 2

Thirty days^a after the administration of MenACYW conjugate vaccine or MENVEO[®] in children 2 to 5 years of age, and in children 6 to 9 years of age, respectively, the hSBA GMTR between Group 1a and Group 2a, and between Group 1b and Group 2b will be calculated and 95% CI will be provided, respectively, as described in Section 5.1.2.2.1.

5.1.2.2.3 For Secondary Objective 3

Thirty days after the administration of MenACYW conjugate vaccine or MENVEO[®] in children 2 to 5 years of age, and in children 6 to 9 years of age, respectively, the difference of hSBA vaccine

^a D30 (+14 days)

seroresponse^a rates between Group 1a and Group 2a, and between Group 1b and Group 2b will be calculated and 95% CI will be provided, respectively, as described in Section 5.1.1.2.

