3.1 Trial Design

This is a Phase III, modified double-blind, randomized, parallel-group, active-controlled, multi-center trial to evaluate the immunogenicity and describe the safety of MenACYW conjugate vaccine compared to the MENVEO[®] in healthy children 2 to 9 years of age in the United States.

Healthy, meningococcal-vaccine naïve children aged 2 to 9 years will be randomized in a 1:1 ratio as follows:

- Group 1: MenACYW conjugate vaccine: N = 500
 - Group 1a: 250 children 2 to 5 years of age^a
 - Group 1b: 250 children 6 to 9 years of age^b
- Group 2: MENVEO[®]: N = 500
 - Group 2a: 250 children 2 to 5 years of age^a
 - Group 2b: 250 children 6 to 9 years of age^b

All subjects will provide blood samples for immunogenicity assessment at baseline (pre-vaccination) and at 30 to 44 days after vaccination.

Solicited adverse event (AE) information will be collected for 7 days after vaccination; unsolicited AE information will be collected from Visit 1 (Day [D] 0) to Visit 2 (D30 [+14 days]) and serious adverse event (SAE) information [REDACTED] will be collected throughout the study period from D0 through D180 (+14 days) after vaccination.

Medically-attended adverse events (MAAEs) will be collected throughout the study from Visit 1 through Visit 2 (as part of the collection of unsolicited AE information) and from Visit 2 through D180 (+14 days) (as MAAEs).

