4.4.2 Immunogenicity

4.4.2.1 Computed Values for Analysis

In order to appropriately manage extreme values ($< \text{LLOQ}$ and $\geq \text{ULOQ}$) for analysis purposes, the following computational rule is applied to the values provided in the clinical database for each blood sample (BL) drawn:

- If a value is $< \text{LLOQ}$, then use the computed value $\text{LLOQ}/2$
- If a value is between $\geq \text{LLOQ}$ and $< \text{ULOQ}$, then use the value
- If a value is $\geq \text{ULOQ}$, then use the computed value ULOQ

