4.4.2.4 A, C, Y, W Seroresponse

hSBA vaccine seroresponse for serogroups A, C, Y, and W is defined as:

- For a subject with a pre-vaccination titer $< 1:8$, the post-vaccination titer must be $\geq 1:16$.
- For a subject with a pre-vaccination titer $\geq 1:8$, the post-vaccination titer must be at least 4-fold greater than the pre-vaccination titer.

rSBA vaccine seroresponse for serogroups A, C, Y, and W is defined as:

- Post-vaccination rSBA titers $\geq 1:32$, if pre-vaccination rSBA titers $< 1:8$ or
- At least a 4-fold increase in rSBA titers from pre- to post-vaccination, if pre-vaccination rSBA titers $\geq 1:8$.

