5.1.3.2 Statistical Methods

5.1.3.2.1 Immunogenicity

Descriptive statistics will be provided for the antibody titers against meningococcal serogroups contained in MenACYW conjugate vaccine and MENVEO[®].

In general, categorical variables will be summarized and presented by frequency counts, percentages, and CIs. The 95% CIs of point estimates will be calculated using the normal approximation for quantitative data and the exact binomial distribution (Clopper-Pearson method) for percentages. For GMTs, 95% CIs of point estimates will be calculated using normal approximation assuming they are log-normally distributed.

Reverse cumulative distribution curve (RCDC) figures will be provided for the antibody titers against meningococcal serogroups contained in MenACYW conjugate vaccine and MENVEO[®] treatment groups.

Descriptive analyses on A, C, Y, and W serogroups on D0 and D30 (+14 days) using hSBA will include but not be limited to:

- GMT and 95% CI in Group 1, Group 2, Group 1a, Group 1b, Group 2a, and Group 2b
- Titer distribution and RCDC
- Percentage of subjects with titer $\geq 1:4$ and $\geq 1:8$ and 95% CI in Group 1, Group 2, Group 1a, Group 1b, Group 2a, and Group 2b
- Percentage of subjects with titer ≥ 4 -fold rise from pre-vaccination to post-vaccination, and 95% CI in Group 1, Group 2, Group 1a, Group 1b, Group 2a, and Group 2b
- Percentage of subjects with hSBA vaccine seroresponse¹³ and 95% CI in Group 1, Group 2, Group 1a, Group 1b, Group 2a, and Group 2b

Descriptive analyses on A, C, Y, and W serogroups on D0 and D30 (+14 days) using rSBA will include but not be limited to:

^a The hSBA vaccine seroresponse for serogroups A, C, Y, and W is defined as:

- For a subject with a pre-vaccination titer $< 1:8$, the post-vaccination titer must be $\geq 1:16$.
- For a subject with a pre-vaccination titer $\geq 1:8$, the post-vaccination titer must be at least 4-fold greater than the pre-vaccination titer.

- GMT and 95% CI in a subset of 200 subjects in Group 1 and Group 2, and in a subset of 100 subjects in Group 1a, Group 1b, Group 2a, and Group 2b
- Titer distribution and RCDCs
- Percentage of subjects with titer $\geq 1:8$ and $\geq 1:128$ and 95% CI in a subset of 200 subjects in Group 1 and Group 2, and in a subset of 100 subjects in Group 1a, Group 1b, Group 2a, and Group 2b

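### The GMT ratio intervals for Secondary Objectives 1 and 2 ignore the baseline titre (and, for Objective 1, the age band), so they are wider than they need be if these predict the response

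*SAP*

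**What the plan says.** SAP 5.1.2.2.1 says that 30 days after vaccination "the hSBA geometric mean titer ratio (GMTR) between Group 1 and Group 2 will be calculated and 95% CI will be provided as follows". The formula is the difference in mean log10 titre, plus or minus a t quantile on n1+n2-2 degrees of freedom times the pooled SD times sqrt(1/n1 + 1/n2). It has no covariate and no stratum term. Section 5.1.2.2.2 applies it by age band: "the hSBA GMTR between Group 1a and Group 2a, and between Group 1b and Group 2b will be calculated".

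The data for an adjusted comparison are already planned:

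- Section 3.1: "All subjects will provide blood samples for immunogenicity assessment at baseline (pre-vaccination) and at 30 to 44 days after vaccination".
- Section 3.1 fixes the age composition of each arm, for example "Group 1a: 250 children 2 to 5 years of age", with the same number in the older band and in the comparator arm.
- Section 4.4.2.4 classifies each child's seroresponse from the pre-vaccination titre, so the primary endpoint depends on the baseline value.
- Section 4.4.2.1 gives a usable number for results outside the quantifiable range: "the following computational rule is applied to the values provided in the clinical database for each blood sample (BL) drawn".

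On the status of the secondary objectives, section 5.1.2.1 says "No hypotheses will be tested. Descriptive statistics will be presented". Section 5.1.4 adds GMTs by age group, gender and race, but no adjusted ratio.

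**The concern.** The GMT ratio is the only direct comparison of titre level between the two vaccines. With no test or margin attached, its interval is all that the reader has to judge it by. If baseline titre or age band predicts the post-vaccination titre, the variation they explain stays in the pooled variance and widens the interval. The SAP collects both variables and uses both elsewhere, but leaves them out here.

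Only precision is at stake. The planned interval is not biased and no success criterion depends on it. Age band matters only for Objective 1, because Objective 2 is already split by age.

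**Working it through.** **No plan figure to reproduce.** The SAP gives no SD, baseline correlation, age effect or target interval width for the GMT ratio, and the text of its sample-size section (5.5) is redacted. The inputs below are therefore assumptions, except the design of two arms by two age bands.

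**Inputs.** 225 evaluable children per arm and age band (250 planned); SD 0.6 log10; LLOQ 1:4; post-vaccination mean near 1:32; 60% of baselines below LLOQ (range 40 to 80%); missing baselines 0 or 3%.

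**Closed form.** Adjusting for baseline multiplies the standard error (SE) by about sqrt(1 - r²), where r is the correlation of the recorded titres. Two age bands of equal size whose means differ by d SDs inflate the unadjusted variance by 1 + d²/4. Rounding to 2-fold steps and setting values below LLOQ to LLOQ/2 weaken the correlation: an underlying 0.3 becomes about 0.25 as recorded, and 0.5 becomes about 0.42.

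- Baseline alone, underlying 0.3: sqrt(1 - 0.25²) = 0.968.
- Baseline alone, underlying 0.5: sqrt(1 - 0.42²) = 0.908.
- Age alone, d = 0.3: sqrt(1/1.0225) = 0.989.
- Both at 0.3: sqrt(0.9375/1.0225) = 0.958.
- Both at 0.5: sqrt(0.8236/1.0625) = 0.880.

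**Simulation.** 3,000 trials per setting (1,500 for the LLOQ and SD ranges), with the rounding and LLOQ rule applied. Entries are the ANCOVA SE divided by the planned SE. For Objective 1 the first column is both the underlying baseline correlation and the age effect in SD; for Objective 2 it is the baseline correlation only.

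| Value | Obj. 1, complete | Obj. 1, 3% missing | Obj. 2, complete | Obj. 2, 3% missing |
|---|---|---|---|---|
| 0 | 1.0005 | 1.0160 | 1.0012 | 1.0163 |
| 0.2 | 0.9818 | 0.9969 | 0.9870 | 1.0023 |
| 0.3 | 0.9584 | 0.9727 | 0.9693 | 0.9837 |
| 0.4 | 0.9254 | 0.9393 | 0.9441 | 0.9585 |
| 0.5 | 0.8819 | 0.8949 | 0.9095 | 0.9230 |

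The missing-data columns are close to the complete ones times sqrt(1/0.97) = 1.015. Break-even is therefore near 0.2 when 3% of baselines are missing.

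**Interval width.** Under the SAP formula with 450 per arm and SD 0.6, the half-width is 1.963 × 0.6 × sqrt(2/450) = 0.0785 log10, a factor of 1.198. In the simulation, rounding, the LLOQ floor and the age effect make it 1.195 at 0.3 and 1.199 at 0.5. With complete baselines:

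- Objective 1: 1.195 becomes 1.186 at 0.3, and 1.199 becomes 1.173 at 0.5. For an observed ratio of 1.00 at 0.3, the interval 0.837 to 1.195 becomes 0.843 to 1.186.
- Objective 2: 1.287 becomes 1.277 at 0.3, and 1.289 becomes 1.259 at 0.5.

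**Equivalent sample size, Objective 1.** 1/0.9584² - 1 = 8.9% and 1/0.8819² - 1 = 28.6% with complete baselines; 1/0.9727² - 1 = 5.7% and 1/0.8949² - 1 = 24.9% with 3% missing.

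**Sensitivity, Objective 1.** With 40% versus 80% of baselines below LLOQ the ratio is 0.953 versus 0.968 at 0.3, and 0.865 versus 0.910 at 0.5. With 80% below LLOQ and 3% missing it is 1.001 at 0.2, 0.982 at 0.3 and 0.923 at 0.5. An SD of 0.5 or 0.7 leaves the ratio at 0.959 or 0.958 at 0.3; only the planned factor moves (1.164 or 1.225).

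**Validity.** Coverage for Objective 1 was 94.2 to 96.1% for the planned interval and 94.3 to 95.8% for the adjusted one (Monte Carlo SE 0.4 to 0.6 points). At 0.3 the two point estimates differ by a median factor of 1.015 (95th percentile 1.046).

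**The case against.** The strongest reply is that nothing here is wrong. The interval is valid and fully specified, the objective is descriptive, and a ratio that can be read straight off the GMT table is easy to explain. The gain cannot be established from the SAP. These children are vaccine-naive, so many baselines may sit below LLOQ, and the gain may differ between serogroups. The Objective 1 column raises two effects together; age alone is worth only about 1% at 0.3 SD, and Objective 2 already reports by age. With weak prediction and some missing baselines, the adjusted interval is slightly wider. On this view an adjusted ratio should be supportive at most.

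Much of this stands. It limits the point to an optional improvement and makes the size conditional. It does not remove the point:

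- For a descriptive comparison, precision is what the interval offers.
- The loss in the null case is 1.6% of the SE under the assumed 3% missing, against a gain of 4 to 12% with complete baselines at moderate values (3 to 11% with 3% missing).
- A gain remains at 80% below LLOQ once the correlation and age effect reach 0.3.
- A single linear baseline slope with 60% of values at LLOQ/2 did not harm coverage.
- Keeping the planned ratio as supportive preserves its readability.

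**Conclusion.** The concern holds as a low-priority point about efficiency. The SAP fixes an unadjusted GMT ratio interval although baseline titre and age band are available and used elsewhere. With complete baselines, adjustment would cut the SE for Objective 1 by about 4% at 0.3 and 12% at 0.5, and for Objective 2 by about 3% and 9%. There is no gain if neither variable is prognostic, and a small loss below a value of about 0.2 if 3% of baselines are missing. All these sizes rest on assumed SD, correlation, age effect, LLOQ, share below LLOQ and evaluable numbers. The primary analysis and the trial's conclusions are unaffected.

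**What to change.** In 5.1.2.2.1, prespecify for each serogroup an ANCOVA of post-vaccination log10 titre on vaccine group, log10 baseline titre (the computed value of 4.4.2.1) and age band. In 5.1.2.2.2, fit the model within each band on vaccine group and log10 baseline titre. In both, back-transform the vaccine-group coefficient and its 95% CI. Name this as the main GMT ratio, and report the planned unadjusted ratio as supportive. Leave the primary seroresponse interval and decision rule as they are.

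Two statements should go with it:

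- The number of children per group without a valid baseline titre. Section 5.3.2 does not impute, so they drop out of the adjusted model; they cannot be classified for seroresponse either. Section 5.2.3 names a missing post-dose sample, but not a missing baseline sample, as a per-protocol exclusion, so such children may stay in the planned ratio. If its criterion on valid test results also covers the baseline sample, the loss is smaller.
- A note that the adjusted ratio will not equal the ratio of the group values reported under 5.1.3.2.1 ("GMT and 95% CI in Group 1, Group 2, Group 1a, Group 1b, Group 2a, and Group 2b").

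The cost is SAP wording and slightly more programming.

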5.1.3 Statistical Methods for Observational Objectives

5.1.3.1 Hypothesis

No hypotheses will be tested. Descriptive statistics will be presented.

5.1.3.2 Statistical Methods

5.1.3.2.1 Immunogenicity

Descriptive statistics will be provided for the antibody titers against meningococcal serogroups contained in MenACYW conjugate vaccine and MENVEO[®].

In general, categorical variables will be summarized and presented by frequency counts, percentages, and CIs. The 95% CIs of point estimates will be calculated using the normal approximation for quantitative data and the exact binomial distribution (Clopper-Pearson method) for percentages. For GMTs, 95% CIs of point estimates will be calculated using normal approximation assuming they are log-normally distributed.

Reverse cumulative distribution curve (RCDC) figures will be provided for the antibody titers against meningococcal serogroups contained in MenACYW conjugate vaccine and MENVEO[®] treatment groups.

Descriptive analyses on A, C, Y, and W serogroups on D0 and D30 (+14 days) using hSBA will include but not be limited to:

- GMT and 95% CI in Group 1, Group 2, Group 1a, Group 1b, Group 2a, and Group 2b
- Titer distribution and RCDC
- Percentage of subjects with titer $\geq 1:4$ and $\geq 1:8$ and 95% CI in Group 1, Group 2, Group 1a, Group 1b, Group 2a, and Group 2b
- Percentage of subjects with titer ≥ 4 -fold rise from pre-vaccination to post-vaccination, and 95% CI in Group 1, Group 2, Group 1a, Group 1b, Group 2a, and Group 2b
- Percentage of subjects with hSBA vaccine seroresponse¹³ and 95% CI in Group 1, Group 2, Group 1a, Group 1b, Group 2a, and Group 2b

Descriptive analyses on A, C, Y, and W serogroups on D0 and D30 (+14 days) using rSBA will include but not be limited to:

^a The hSBA vaccine seroresponse for serogroups A, C, Y, and W is defined as:

- For a subject with a pre-vaccination titer $< 1:8$, the post-vaccination titer must be $\geq 1:16$.
- For a subject with a pre-vaccination titer $\geq 1:8$, the post-vaccination titer must be at least 4-fold greater than the pre-vaccination titer.

- GMT and 95% CI in a subset of 200 subjects in Group 1 and Group 2, and in a subset of 100 subjects in Group 1a, Group 1b, Group 2a, and Group 2b
- Titer distribution and RCDCs
- Percentage of subjects with titer $\geq 1:8$ and $\geq 1:128$ and 95% CI in a subset of 200 subjects in Group 1 and Group 2, and in a subset of 100 subjects in Group 1a, Group 1b, Group 2a, and Group 2b
- Percentage of subjects with titer ≥ 4 -fold rise from pre-vaccination to post-vaccination and 95% CI in a subset of 200 subjects in Group 1 and Group 2, and in a subset of 100 subjects in Group 1a, Group 1b, Group 2a, and Group 2b
- Percentage of subjects with rSBA vaccine seroresponse^a and 95% CI in a subset of 200 subjects in Group 1 and Group 2, and in a subset of 100 subjects in Group 1a, Group 1b, Group 2a, and Group 2b

5.1.3.2.2 Safety

Safety results in [Section 4.3.2.2](#) will be described for subjects in all study groups. The main parameters for the safety endpoints will be described by 95% CIs (Clopper-Pearson method) (6). Analyses will contain at least the descriptions listed in [Table 5.2](#):

Table 5.2: Statistical analyses for safety observational objective

Safety Events	Time and Group	Description
Immediate unsolicited systemic AE	Within 30 minutes after injection for all subjects in Groups 1 and 2 at D0	Percentage of subjects that have the event, MedDRA terms, intensity, relationship to vaccine, study discontinuation
Solicited injection site reactions	Up to 7 days after D0 for all subjects in Groups 1 and 2	Percentage of subjects that have the event, onset, duration, intensity, action taken, study discontinuation, temperature collection routes
Solicited systemic reactions	Up to 7 days after D0 for all subjects in Groups 1 and 2	
Unsolicited AE	Up to 30 days after D0 for all subjects in Groups 1 and 2	Percentage of subjects that have the event, MedDRA terms, onset, duration, intensity, relationship, action taken, study discontinuation

^a rSBA vaccine seroresponse is defined as a post-vaccination titer $\geq 1:32$ for subjects with pre-vaccination rSBA titer $< 1:8$, or a post-vaccination titer ≥ 4 times the pre-vaccination titer for subjects with pre-vaccination rSBA titer $\geq 1:8$.

SAE [REDACTED]	Up to 6-month follow-up after D0 for all subjects in Groups 1 and 2	Percentage of subjects that have the event, MedDRA terms, onset, duration, relationship, seriousness criteria, outcome, study discontinuation
MAAE	Between Visit 1 and Visit 2 for all subjects in Groups 1 and 2 (as unsolicited AE) From Visit 2 to 6-month follow-up for all subjects in Groups 1 and 2	Percentage of subjects that have the event, MedDRA terms, onset, duration, intensity, relationship, action taken, study discontinuation

5.1.4 Complementary Output

Additional analyses by age group, gender, and race will be provided in Appendix 15 of the CSR.

Immunogenicity analyses:

- hSBA GMTs and 95% CI at each time point for each group – Per-Protocol Analysis Set
- Vaccine seroresponse against meningococcal serogroups A, C, Y, and W measured by hSBA and 95% CI – Per-Protocol Analysis Set
- rSBA GMTs and 95% CI at each time point for each group – Per-Protocol Analysis Set
- Vaccine seroresponse against meningococcal serogroups A, C, Y, and W measured by rSBA and 95% CI – Per-Protocol Analysis Set

Safety analyses:

Safety overview after injection – Safety Analysis Set

5.2 Analysis Sets

Three analysis sets will be used: the Full Analysis Set (FAS), the Per-Protocol Analysis Set (PPAS), and the Safety Analysis Set (SafAS).

5.2.1 Full Analysis Set

The FAS is defined as the subset of subjects who received at least one dose of the study vaccine and had a valid post-vaccination serology result. All subjects will be analyzed according to the treatment group to which they were randomized.

5.2.2 Safety Analysis Set

The SafAS is defined as those subjects who have received study vaccine^a and have any safety data available. All subjects will have their safety analyzed according to the vaccine they actually received.

Safety data recorded for a vaccine received out of the protocol design will be excluded from the analysis (and listed separately).

5.2.3 Per-Protocol Analysis Set

The PPAS is a subset of the FAS. The subjects presenting with at least one of the following relevant protocol deviations will be excluded from the PPAS:

- Subject did not meet all protocol-specified inclusion criteria or met at least one of the protocol-specified exclusion criteria
- Subject did not receive vaccine
- Subject received a vaccine other than the one that he / she was randomized to receive
- Preparation and / or administration of vaccine was not done as per-protocol
- Subject did not receive vaccine in the proper time window
- Subject did not provide the post-dose serology sample in the proper time window or a post-dose serology sample was not drawn. The time window will be defined as D30 to D44 (D30 +14 days) post-vaccination.
- Subject received a protocol-prohibited Category 2 or Category 3 therapy / medication / vaccine, as defined in Section 6.7 of the protocol.
- Subject's serology sample did not produce a valid test result
- Subject had other protocol violations that affected the subject's immune response, as determined by the clinical team before locking the database.

5.2.4 Populations Used in Analyses

All immunogenicity analyses will be performed on the PPAS. Additional immunogenicity analyses will be performed for exploratory purposes on the FAS. In the FAS, subjects will be analyzed by the vaccine group to which they were randomized.

All safety analyses will be performed on the SafAS. Subjects will be analyzed according to the vaccine they actually received.

^a For which safety data are scheduled to be collected

5.3 Handling of Missing Data and Outliers

5.3.1 Safety

No replacement will be done. In all subject listings, partial and missing data will be clearly indicated as missing.

